1.0 Introduction

In randomized controlled trials, randomization ensures that the different arms of the trial tend to be balanced, both in terms of measured and unmeasured characteristics of the population. Thus, the only systematic difference between treated and untreated patients is the exposure to treatment. This allows one to obtain unbiased estimates of the average treatment effect within the context of the study design. In the studies such that the treatment effect will be estimated with the combination of in-trial placebo subjects and historical placebo subjects, the distribution of subject characteristics is likely to vary systematically between the in-trial subjects and historical subjects and is often related to patient prognosis, patient characteristics, and physician preference. Thus, confounding may occur.

Propensity score matching method (Rosenbaum and Rubin, 1985) matches in-trial patients with synthetic placebo subjects based on propensity scores such that matched in-trial subjects and placebo subjects are comparable in terms of covariates used in propensity score determination. This process mimics randomization to create two comparable groups with a caution of limitation that the matching is conditional on included covariates.

To provide the guidance on how many synthetic placebo subjects can be matched for the primary and secondary analysis (HiSCR and NRS30), simulations have been conducted to evaluate the power and false positive rate of combining the data from historical placebo subjects and in-trial subjects under different scenarios.

2.0 Methods

The simulation procedures are outlined in the following sections.

2.1 Simulation of Baseline Covariates and Treatment Groups

Within each simulation, the following baseline covariates were generated for the 68 in-trial subjects from multivariate normal distribution:

- Age
- Baseline AN count
- Baseline BMI
- Duration of HS since diagnosis
- Baseline draining fistula
- Gender
- Race
- Smoking status

The multivariate normal distribution with mean vector μ , standard deviation S and correlation matrix Σ is defined as below (covariates in the order as listed above):

$$\mu' = (35.8, 21.8, 35.2, 11, 3.56, 0, 0, 0)$$

$$S' = (11.91, 20.73, 8.65, 8.4, 5.14, 1, 1, 1)$$

$$\Sigma = \begin{pmatrix} 1 & 0 & 0 & 0.4 & 0.1 & 0 & 0 & 0 \\ 0 & 1 & 0.1 & 0 & 0.3 & 0 & 0 & 0 \\ 0 & 0.1 & 1 & 0 & 0 & 0 & 0 & 0 \\ 0.4 & 0 & 0 & 1 & 0 & 0 & 0 & 0 \\ 0.1 & 0.3 & 0 & 0 & 1 & 0 & 0 & 0 \\ 0 & 0 & 0 & 0 & 0 & 1 & 0 & 0.1 \\ 0 & 0 & 0 & 0 & 0 & 0 & 1 & 0.2 \\ 0 & 0 & 0 & 0 & 0 & 0.1 & 0.2 & 1 \end{pmatrix}$$

The means and standard deviations for the continuous variables were estimated based on the baseline information from the in-trial subjects. For the binary variables, random

samples were generated using standard normal distribution and the binary outcome of 0 or 1 was determined by the proportions estimated from the in-trial subjects.

Based on the baseline information from 68 in-trial subjects, the two stratification factors, baseline Hurley Stage (<III, III), and the indicator of prior exposure to anti-TNF treatment (Yes, No) were generated assuming that 5% of the subjects are Hurley Stage <III and have prior exposure to anti-TNF treatment, 10% of the subjects are Hurley Stage III and have prior exposure to anti-TNF treatment, 55% of the subjects are Hurley Stage <III and do not have prior exposure to anti-TNF treatment, and 35% of the subjects are Hurley Stage III and do not have prior exposure to anti-TNF treatment.

Treatment groups (upadacitinib 30 mg and placebo) were generated in a 2:1 ratio within each of the 4 strata. With a total of 68 subjects, it was assumed that 45 subjects received upadacitinib 30 mg, and 23 subjects received placebo.

2.2 Matching Historical Placebo Subjects Using Propensity Score

In the matching phase, placebo subjects from existing studies (Study M11-313, Study M11-810, Study M16-833) were matched in a fixed ratio with in-trial subjects using propensity score method with pre-selected baseline covariates. Nearest neighbor matching method was used.

Different numbers of matched subjects were evaluated:

Number of Matched Subjects	Matching Ratio (in-trial: matching)	Control Set
23	1:1	In-trial placebo subjects (N=23)
46	1:2	In-trial placebo subjects (N=23)
68	1:1	All in-trial subjects (N=68)

3.0 Scenarios and Simulation Results for Primary Endpoint (HiSCR) and Secondary Endpoint (NRS30)

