9.0 Efficacy Analyses

9.1 General Considerations

All efficacy analyses will be conducted in ITT Population in each period. All tests will be 1-sided at an alpha level of 0.05.

The Primary Analysis will be conducted after all ongoing subjects have completed Week 12, data pertaining to Period 1 has been cleaned, and a database lock has occurred for the purpose of efficacy and safety analysis in Period 1. This is the only and final efficacy analysis for Period 1.

In Period 1, all categorical variables at Week 12 and experience of flare in Period 1 will be analyzed using one sample Chi-square test comparing with historical placebo rate. Supplemental analyses will be conducted to compare in-trial data in upadacitinib group vs in-trial placebo data combined with historical placebo data for primary and secondary endpoints, and compare in-trial data in upadacitinib group vs in-trial placebo data for all categorical endpoints.

Continuous variables will be analyzed using Mixed-Effect Model Repeat Measurement (MMRM) (for endpoints other than DLQI) and Analysis of Covariance (ANCOVA) (for

DLQI) comparing with historical placebo mean change from Baseline at Week 12. Supplemental analyses will be conducted to compare in-trial data in upadacitinib group vs in-trial placebo data.

Long-term efficacy in the Period 2 will be summarized using the observed case approach.

Any subject who is randomized based on a wrong stratum will be analyzed according to the actual stratum the subject belongs to.

For variables other than PGA Skin Pain NRS, "Baseline" refers to the last non-missing observation on or before the date of the first administration of study drug or the date of randomization if no study drug is given. The "Baseline" of PGA Skin Pain NRS is defined as the last non-missing weekly average score, calculated based on the daily scores from the past 7 days (with non-missing values in 4 or more days of the 7 day period), before the date of the first administration of study drug or on or before the date of randomization if no study drug is given.

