9.3.3 Sensitivity Analyses of the Primary Efficacy Endpoint

Historical placebo data pre-selected by propensity score matching combined with in-trial placebo data will be used to estimate treatment effect of upadacitinib against placebo. Subjects with historical placebo data of HiSCR were pre-selected using propensity score matching from two Humira Phase 3 studies (M11-313 and M11-810) and the Risankizumab study (M16-833), whose study populations, entry criteria and study designs are similar to this study.

The propensity scores were estimated for all randomized subjects in this study and historical placebo subjects with selected common baseline demographics and characteristics variables:

- Age
- Gender
- Race
- Smoking status
- Baseline BMI

- Baseline AN count (abscess count and inflammatory nodule count)
- Duration of HS since diagnosis
- Baseline Hurley Stage
- Baseline draining fistula

The "nearest neighbor matching" were performed based on a distance measure, caliper, with the propensity score for each subject calculated from the logistic regression. The number of synthetic placebo subjects was determined by the simulation results, for each in-trial placebo rate assumption, with pre-determined criteria that the number of synthetic placebo subjects not to exceed 68 (approximately 3 times the number of in-trial placebo subjects) and the one-sided false positive rate was controlled at 10% (simulation details can be found in [Appendix F](#) and the list of matching subjects can be found in [Appendix G](#):

In-Trial Placebo Rate	Number of Synthetic Placebo Subjects
≤ 33%	68
>33% and ≤ 34%	23*
>34%	0

* The 23 subjects with the highest rank in [Appendix G](#) Table A will be used in the analysis.

After database lock, comparison between the in-trial data of the upadacitinib group and the in-trial placebo data combined with the pre-selected historical placebo subjects' data will be performed. Frequencies and percentages will be summarized along with 95% confidence interval (CI). Pairwise comparisons of upadacitinib vs. placebo will be made using CMH test. Point estimates, *p*-value and 95% CIs for the difference in proportions between each upadacitinib group and placebo will be provided. The stratification factors (prior exposure to anti-TNF [yes, no], Hurley Stage [$<$ III, III]) will be adjusted in the model.

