3.1 HiSCR

Different scenarios with regard to the variations in the in-trial placebo rate relative to the historical placebo rate (28%) were considered: in-trial placebo subjects perform worse than historical placebo subjects by 10% or 5%, in-trial placebo subjects perform similarly as the historical placebo subjects, and in-trial placebo subjects perform better than historical placebo subjects by 5% or 10%, as summarized in the following table.

Scenario	Placebo Rate	Upadacitinib Rate*
In-trial PBO rate = Historical rate -10%	0.18	0.59
In-trial PBO rate = Historical rate - 5%	0.23	0.59
In-trial PBO rate = Historical rate	0.28	0.59
In-trial PBO rate = Historical rate + 5%	0.33	0.59
In-trial PBO rate = Historical rate + 10%	0.38	0.59

* Assume that upadacitinib performs at least as good as min TPP.

One-sided power and false positive rates for each scenario and different numbers of matched subjects were calculated, and the results from 10000 simulations (random seed: 12345) are summarized in the following table:

	Power				False Positive Rate			
	Number of Matched Subjects			In-Trial Only	Number of Matched Subjects			In-Trial Only
Scenario	23	46	68	UPA vs PBO: 45:23	23	46	68	UPA vs PBO: 45:23
In-trial PBO rate = Historical rate - 10%	0.978	0.984	0.984	0.977	0.013	0.004	0.002	0.082
In-trial PBO rate = Historical rate - 5%	0.957	0.973	0.977	0.926	0.027	0.014	0.009	0.075
In-trial PBO rate = Historical rate	0.925	0.954	0.966	0.837	0.051	0.04	0.033	0.072
In-trial PBO rate = Historical rate + 5%	0.877	0.933	0.951	0.701	0.087	0.093	0.091	0.07
In-trial PBO rate = Historical rate + 6%*	0.865	0.927	0.948	0.672	0.095	0.105	0.108	0.07
In-trial PBO rate = Historical rate + 10%	0.811	0.904	0.935	0.549	0.133	0.168	0.189	0.069

* To determine the number of matched subjects, additional scenario of historical rate + 6% was also evaluated and the power and false positive rate are given in the table.

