The simulation results show that power with matched placebo subjects from historical data is higher than that with in-trial placebo subjects only in all of the scenarios. Power increases with the increase in the number of matched placebo subjects. In the meantime, when the in-trial placebo rate is lower than or similar to the historical placebo rate, the false positive rates are controlled at approximately 0.05. When the in-trial placebo rate is higher than historical placebo rate, the false positive rate increases with the increase in the number of matched subjects. The inflation in the false positive rate is larger when higher in-trial placebo rate is observed. The number of matched subjects is therefore determined by both achieving a high power and maintaining a slightly inflated false positive rate.

To determine the number of matched placebo subjects in the analysis, the following two criteria should be satisfied:

- One sided false positive rate is controlled at 10%;
- Not to exceed 68 (approximately 3 times the number of in-trial placebo subjects).

The numbers of matched placebo subjects are given in the following table:

In-Trial PBO Rate	Number of Matched Subjects
≤ 33%	68
>33% and ≤ 34%	23
>34%	0

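### The HiSCR borrowing cut-offs were calibrated on historical sets re-matched in simulation, but the analysis uses one fixed list; the 10% false-positive limit then needs at least 19 of 68 responders on that list

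*SAP*

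**What the plan says.** **How the cut-offs were set.** Appendix F 2.1 states: "Within each simulation, the following baseline covariates were generated for the 68 in-trial subjects from multivariate normal distribution". Appendix F 2.2 then says that placebo subjects from the three earlier studies "were matched in a fixed ratio with in-trial subjects using propensity score method with pre-selected baseline covariates". The sets of 23 and 46 are matched 1:1 and 1:2 to the 23 in-trial placebo subjects. The set of 68 is matched 1:1 to all 68 in-trial subjects. In Appendix F 3.1, "variations in the in-trial placebo rate relative to the historical placebo rate (28%) were considered". The criterion is "One sided false positive rate is controlled at 10" per cent, with at most 68 borrowed. The cut-offs follow from the printed table: 68 borrowed gives 0.091 at 33% and 0.108 at 34%, and 23 borrowed gives 0.095 at 34%.

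**What will be analysed.** SAP 9.3.3: "Subjects with historical placebo data of HiSCR were pre-selected using propensity score matching from two Humira Phase 3 studies" and from the risankizumab study, with the list given in Appendix G. For the middle tier, "The 23 subjects with the highest rank in" Appendix G Table A are used. Protocol 7.3 describes the historical placebo data as already unblinded.

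**The concern.** The simulated set and the analysed set are not the same object. If the historical subjects are re-matched to new simulated in-trial subjects in each run, the number of borrowed responders varies between runs and the printed rate is an average. In the analysis that number is one constant, which the sponsor can count. The false-positive rate that applies is the one conditional on that constant, and the SAP shows none.

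The 23-subject set differs in a second way. It was simulated as 1:1 matches to the in-trial placebo subjects, but the analysis takes the top-ranked 23 of the list.

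At stake is the only error limit that the SAP states for the combined-placebo comparison. If the list responds a little below 28%, the rule can borrow 68 subjects where its own limit is exceeded. If a little above, it may discard controls that the limit would allow.

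**Working it through.** **Inputs.** Test level: "All tests will be 1-sided at an alpha level of 0.05" (SAP 9.1), so the critical value is 1.645. Sizes: "it was assumed that 45 subjects received upadacitinib 30 mg, and 23 subjects received placebo" (Appendix F 2.1). Borrowed: 68. Historical rate: 28%, and 0.28 × 68 = 19.04. Limit: 10%. R is the number of HiSCR responders among the 68. It is not in the reviewed text, so it is varied.

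**Method.** Under the null, x1 ~ Binomial(45, p) and x0 ~ Binomial(23, p). Let p1 = x1/45 and p0 = (x0 + R)/91. Reject if (p1 − p0)/√V > 1.645, with either
- unpooled V = p1(1 − p1)/45 + p0(1 − p0)/91, or
- pooled V = q(1 − q)(1/45 + 1/91), where q = (x1 + x0 + R)/136.

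The false-positive rate is the sum of the binomial probabilities over the rejection region. Ranges below span the two variances.

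**Reproducing the printed column (68 borrowed, unpooled V).**

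| True in-trial rate | Printed | R fixed at 19 | R varying, mean 19.04, SD 2 |
|---|---|---|---|
| 23% | 0.009 | 0.005 | 0.008 |
| 28% | 0.033 | 0.026 | 0.031 |
| 33% | 0.091 | 0.083 | 0.091 |
| 34% | 0.108 | 0.100 | 0.108 |
| 38% | 0.189 | 0.191 | 0.199 |

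The SD of 2 was chosen to fit. It matches the two rates that set the cut-off and comes close at 23% and 28%, but not at 38%. This supports the reading that the historical set changed between runs; it does not prove it.

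**Why R matters.** At a true 33%, the expected combined placebo rate is (23 × 0.33 + R)/91. With R = 19 this is 26.59/91 = 29.2%; with R = 18, 28.1%; with R = 17, 27.0%. The null then carries an apparent benefit of 3.8, 4.9 or 6.0 percentage points.

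**List held fixed.** The written rule borrows 68 if the observed placebo rate is at most 33% (7 of 23 or fewer). Otherwise, with 23 subjects and whole responders, it borrows none and compares 45 with 23.

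| R of 68 | 68 always borrowed, true 33% | Written rule, true 33% | Written rule, maximum over true rates |
|---|---|---|---|
| 17 (25.0%) | 0.136-0.148 | 0.095-0.106 | 0.126-0.131 |
| 18 (26.5%) | 0.107-0.113 | 0.078-0.084 | 0.115 |
| 19 (27.9%) | 0.083-0.085 | 0.060-0.062 | 0.096-0.098 |
| 20 (29.4%) | 0.063 | 0.048 | 0.086-0.090 |

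The first results column is Appendix F's own basis. A stratified simulation with several variance estimators gives 0.129-0.150, 0.101-0.113, 0.082-0.090 and 0.060-0.070 for R = 17 to 20 on that basis, so the threshold is again 19. The stratum shares in Appendix F 2.1 add to 105% and were rescaled. The maxima in the last column occur at true rates of roughly 38% to 41%.

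**The 23-subject set.** Held fixed at a true rate of 34% (unpooled V), 5 of 23 responders gives 0.139 and 6 of 23 gives 0.085; the printed rate is 0.095. One responder among the top-ranked 23 decides whether the limit holds.

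**The middle tier.** With 23 placebo subjects, 7/23 = 30.4% and 8/23 = 34.8%, so no whole count falls above 33% and at or below 34%. With 21 or 24 subjects it can: 7/21 = 8/24 = 33.3%.

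**The case against.** The strongest reply is that 33% is a true rate in Appendix F, whereas the rule acts on the observed rate. At a true 33% the written rule gives 0.078-0.084 with 18 responders and 0.095-0.106 with 17, at or near the limit. That is correct, and the threshold of 19 should not be read as describing the written rule at exactly 33%. It does describe Appendix F's own calculation, and the written rule once the limit must hold at every true rate.

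Averaging over matched sets is also a defensible way to calibrate before a list exists. Here the list exists, so the conditional rate can be computed.

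The consequence is limited. The primary test is one-sample against 25%, an in-trial-only comparison is also planned, and the SAP openly accepts a slightly inflated false-positive rate in a proof-of-concept study. All of that stands, and it makes this an inexpensive improvement rather than a serious defect.

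Some stronger readings are tempting but unsupported:
- **That the limit is breached, or that the sponsor ignored a number it held.** The SAP does not say where 28% comes from. Since 19/68 = 27.9%, it could be the list's own rate. Real historical subjects were matched in the simulation, so their recorded outcomes may already enter it.
- **That the list responds at 25%.** That rate (SAP 2.4) comes from the two Humira studies; the borrowed pool covers three.
- **That the list is a random draw at 28%, so that probabilities can be put on R.** The binomial SD is √(68 × 0.28 × 0.72) = 3.7, which gives 0.109-0.121 at 33% rather than the printed 0.091.
- **That the middle tier can never occur.** It can with 21 or 24 placebo subjects, or with fractional rates from the COVID-19 multiple imputation.

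**Conclusion.** The mismatch stands. The simulation matches historical subjects to simulated in-trial subjects, while the analysis uses one fixed, ranked list whose top 23 were not the 23 simulated. On Appendix F's own basis the 10% limit for borrowing 68 needs at least 19 of 68 responders: 18 is a marginal failure (about 0.11) and 17 a clear one (about 0.14). The written rule reaches the same threshold over all true rates. Because 28% of 68 is 19.04, the cut-off has almost no margin.

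This rests on 45:23 subjects, a one-sided 0.05 test, and re-matching in each run, which is inferred from Appendix F 2.1 and 2.2 and only partly confirmed by the printed column. The results for the written rule are unstratified. Their in-trial-only rate at 33% is 0.062 (unpooled V) against the printed 0.07, so the stratified maxima could be slightly higher than shown. Whether the actual list meets the limit cannot be judged from the reviewed text.

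**What to change.** Before unblinding, recompute the HiSCR false-positive rates with the Appendix G Table A list, and its 23 top-ranked subjects, held fixed at their recorded outcomes. Vary only the in-trial outcomes, use the stratified test of SAP 9.3.3, and apply the data-dependent rule across a range of true placebo rates.

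If the rate stays at or below 10%, keep the cut-offs and add a sentence reporting the list's responder count and the conditional rate. If not, reset the cut-offs in SAP 9.3.3 and Appendix F 3.1. State them as in-trial placebo responder counts, for 23 subjects and for nearby group sizes, and say how fractional imputed rates are treated. Keep the middle tier only where it is attainable.

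The cost is a short calculation on data that the sponsor already holds and a wording change before database lock. The downside is that the cut-off may become stricter if the list responds below 28%.

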3.1 HiSCR

Different scenarios with regard to the variations in the in-trial placebo rate relative to the historical placebo rate (28%) were considered: in-trial placebo subjects perform worse than historical placebo subjects by 10% or 5%, in-trial placebo subjects perform similarly as the historical placebo subjects, and in-trial placebo subjects perform better than historical placebo subjects by 5% or 10%, as summarized in the following table.

Scenario	Placebo Rate	Upadacitinib Rate*
In-trial PBO rate = Historical rate -10%	0.18	0.59
In-trial PBO rate = Historical rate - 5%	0.23	0.59
In-trial PBO rate = Historical rate	0.28	0.59
In-trial PBO rate = Historical rate + 5%	0.33	0.59
In-trial PBO rate = Historical rate + 10%	0.38	0.59

* Assume that upadacitinib performs at least as good as min TPP.

One-sided power and false positive rates for each scenario and different numbers of matched subjects were calculated, and the results from 10000 simulations (random seed: 12345) are summarized in the following table:

	Power				False Positive Rate			
	Number of Matched Subjects			In-Trial Only	Number of Matched Subjects			In-Trial Only
Scenario	23	46	68	UPA vs PBO: 45:23	23	46	68	UPA vs PBO: 45:23
In-trial PBO rate = Historical rate - 10%	0.978	0.984	0.984	0.977	0.013	0.004	0.002	0.082
In-trial PBO rate = Historical rate - 5%	0.957	0.973	0.977	0.926	0.027	0.014	0.009	0.075
In-trial PBO rate = Historical rate	0.925	0.954	0.966	0.837	0.051	0.04	0.033	0.072
In-trial PBO rate = Historical rate + 5%	0.877	0.933	0.951	0.701	0.087	0.093	0.091	0.07
In-trial PBO rate = Historical rate + 6%*	0.865	0.927	0.948	0.672	0.095	0.105	0.108	0.07
In-trial PBO rate = Historical rate + 10%	0.811	0.904	0.935	0.549	0.133	0.168	0.189	0.069

* To determine the number of matched subjects, additional scenario of historical rate + 6% was also evaluated and the power and false positive rate are given in the table.

The simulation results show that power with matched placebo subjects from historical data is higher than that with in-trial placebo subjects only in all of the scenarios. Power increases with the increase in the number of matched placebo subjects. In the meantime, when the in-trial placebo rate is lower than or similar to the historical placebo rate, the false positive rates are controlled at approximately 0.05. When the in-trial placebo rate is higher than historical placebo rate, the false positive rate increases with the increase in the number of matched subjects. The inflation in the false positive rate is larger when higher in-trial placebo rate is observed. The number of matched subjects is therefore determined by both achieving a high power and maintaining a slightly inflated false positive rate.

To determine the number of matched placebo subjects in the analysis, the following two criteria should be satisfied:

- One sided false positive rate is controlled at 10%;
- Not to exceed 68 (approximately 3 times the number of in-trial placebo subjects).

The numbers of matched placebo subjects are given in the following table:

In-Trial PBO Rate	Number of Matched Subjects
≤ 33%	68
>33% and ≤ 34%	23
>34%	0

